5.9.2 Allowed Medications

See Section 5.9 for a general discussion of concomitant medications.

5.9.2.1 *Candida Prophylaxis and Concomitant Antifungal Therapy*

F901318 is not active against yeast infections and the use of fluconazole for prophylaxis or treatment of concomitant candidiasis is permitted at any time due to fluconazole's lack of activity against mould fungi. Patients who are receiving treatment with isavuconazole or posaconazole should be switched to receive treatment with fluconazole. Should a patient start or stop receiving fluconazole treatment whilst on study, an extra visit for Unscheduled Trough PK sampling will occur 3 to 5 days after starting or stopping such concomitant medication. This Unscheduled Trough PK sample will be sent for rapid trough PK analysis of F901318, to assess the impact of any dose adjustment made.

In order to meaningfully analyse the efficacy of F901318, it is important to avoid concomitant use of other systemic antifungal agents with known or potential activity against the primary fungal infection. That said, the constraints on choice of additional agents may be complex and thus use of any other systemic concomitant antifungal or combination treatment (such as addition of terbinafine for confirmed *Lomentospora prolificans* infections or an echinocandin to manage infection due to *Candida*) is permitted but is discouraged.

For all other infections, antifungal combinations should be based on the Investigator's clinical judgement with efforts made to minimize use where possible. Use of concomitant antifungal therapy must be discussed and agreed with the MM.

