12. MEDICATIONS

Concomitant and prior Antifungal Medications will be coded using the most recent version of World Health Organisation Drug Dictionary (WHO-DD) and descriptive statistics by ATC level 4 for all concomitant medications

Document: \\weedc-vnasc01\BIOSdata\F2G\F901318\ [Redacted]
Author: [Redacted] Version Number: 3.0
Version Date: 06Apr2023
Template No.: CS_TP_BS016 Revision 6 Reference: CS_WI_BS005
Effective Date: 02Dec2019

and antifungal concomitant medications based on the ITT analysis set will be presented.

See [appendix 2](#) for handling of partial dates for medications, in the case where it is not possible to define a medication as prior, concomitant or post the medication will be classified by the worst case; i.e. concomitant. A medication may be classed as both 'prior' and 'concomitant'.

- 'Prior' medications are medications which were started prior to the first dose of study medication.
- 'Concomitant' medications are medications which were:

started prior to, on or after the first dose of study medication but prior to last dose of study medication,

AND ended on or after the date of first dose of study medication or were ongoing at the end of the study.

- 'Post' medications are medications started after the last dose of study medication (to be listed only).
- Therapeutic drug monitoring data on medications resulting in dose adjustments will be listed.
- Concomitant antifungal usage (Yes/No)
 - number of days of concomitant antifungal usage on study
- Summary will be presented by systemic antifungal medication and non-antifungal medications. Systemic antifungals will be confirmed and provided by medical review process.
- Plot for duration of antifungal medications will also be presented.

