16.1. PRIMARY EFFICACY

16.1.1. PRIMARY EFFICACY VARIABLE & DERIVATIONS

The primary efficacy variable is the DRC-adjudicated overall response at Day 42, as determined by an independent DRC using a combination of clinical, mycological and radiological results, and collected in a separate DRC adjudicated outcome database.

Table A presents the criteria for invasive fungal disease assessment of overall response.

Table A: Criteria for IFD assessment of overall response

Overall Response	Criteria
Success-Complete*:	
 Clinical: Meets Criteria for Resolution Complete; Radiological (if assessed): Shows resolution of radiological abnormalities ($\geq 90\%$ response); Mycological: Meets criteria for presumed or documented eradication.
Success-Partial*:	
 Clinical: Meets Criteria for Resolution-Complete or Resolution-Partial; Radiological: Shows resolution or improvement of radiological abnormalities (at least 25% response); Mycological: Meets criteria for presumed or documented eradication.
Failure-Stable:	
 Clinical: No improvement and no worsening of any attributable clinical symptoms and physical findings previously noted and no new attributable clinical symptoms or physical findings of IFD (Failure-Stable); 
OR
 
 Radiological (if assessed): Shows no evidence of progression OR $< 25\%$ improvement of radiological abnormalities; 
OR
 
 Mycological: Had mycological evidence at baseline AND does not meet criteria for presumed or documented eradication.
Failure-Progression:	
 Clinical: Either worsening of attributable clinical symptoms or physical findings of IFD or appearance of new attributable symptoms or findings of IFD (Failure-Progression); 
OR
 
 Radiological: Worsening or new radiological abnormalities; 
OR
 
 Mycological: Has mycological evidence for a recurrent or emergent IFD, OR alternative systemic antifungal treatment required.

Document: \\weedc-vnasc01\BIOSdata\F2G\F901318\

Author:

Version Number:

3.0

Version Date:

06Apr2023

Template No.: CS_TP_BS016 Revision 6

Reference: CS_WI_BS005

Effective Date: 02Dec2019

F2G Ltd.
PROTOCOL F901318/0032

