*For these categories, the only required data are the clinical and mycological data. The absence of radiological evaluations at a given time point does not prevent assignment to Success-Complete or Success-Partial. The rules defining success are tested in sequence with Success-Complete assigned if its rules are met and Success-Partial otherwise assigned. The rules for Failure are tested next and Failure is assigned if any of its rules are met. The rules for Stable are tested last.

Number and % of patients will be summarised for the 4 categories shown in Table A. N and % will also be summarised for the 3 categories of Success (Success-Complete, Success-Partial), Stable disease (Failure-Stable) and Failure (Failure-Progression, Death, and those patients for whom data at Day 42 cannot be collected or who are considered not evaluable at Day 42).

For statistical primary analysis of overall response rate, values will be assigned to the DRC-adjudicated overall response as follows:

- Success (Success-Complete, Success-Partial),
- Failure (Failure-Stable, Failure-Progression, Death, and those patients for whom data at Day 42 cannot be collected or who are considered not evaluable at Day 42). Patients withdrawn from study medication due to an unsuccessful overall outcome are required per protocol to return for the main study phase EOT visit but will not be asked to return for the Day 42 and/or Day 84 visits; these patients will be considered as failures at all subsequent timepoints.

As a key important analysis, patients with a stable disease outcome will be considered a success, i.e. assigning the DRC adjudicated response to categories as follows.

- Success (Success-Complete, Success-Partial, Failure-Stable)
- Failure (Failure-Progression, Death, and those patients for whom data at Day 42 cannot be collected or who are considered not evaluable at Day 42)

This alternative classification, where stable disease outcome can be considered a successful response in the timeframe of this evaluation, is an important analysis due to the nature of this challenging patient population for whom other therapies have already failed.

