16.1.4. SENSITIVITY ANALYSIS OF PRIMARY EFFICACY VARIABLE

The primary efficacy analysis will be repeated for the PPAS.

Additionally, a sensitivity analysis of modified overall response will be performed for the mITT population where success will be defined as follows:

Modified Overall Response	Criteria
Success :	
• Clinical: Meets Criteria for Resolution-Complete or Resolution-Partial;• Radiological (if assessed): Shows no change or improvement of radiological abnormalities ($\geq 0\%$ response);• Mycological: Meets criteria for presumed or documented eradication.

The only required data are the clinical and mycological data. The absence of radiological evaluations at a given time point does not prevent assignment to Modified Overall Response as Success.

Similar to the primary analysis, a response rate will be calculated for the proportion of successes. A 95% exact Clopper-Pearson CI for the single binomial proportion will be calculated.

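### No planned analysis relates add-on mould-active antifungals to Day 42 response, although the protocol treats such use as a threat to interpreting efficacy

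*Protocol*

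**What the plan says.** Protocol 5.9.2.1, with matching text in the synopsis, gives the reason for restricting co-therapy: if efficacy is to be analysed meaningfully, "it is important to avoid concomitant use of other systemic antifungal agents with known or potential activity against the primary fungal infection". It then says that "use of any other systemic concomitant antifungal or combination treatment" "is permitted but is discouraged", and adds a condition: "Use of concomitant antifungal therapy must be discussed and agreed with the MM".

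In the SAP, "The primary efficacy variable is the DRC-adjudicated overall response at Day 42" (16.1.1). Complete and partial responses are the successes. They rest on clinical and mycological criteria, plus radiology if it was assessed. Concomitant antifungal use is not among the conditions. The nearest rule is in the Failure-Progression row of SAP Table A and Protocol Table 5, which applies when alternative systemic antifungal treatment is needed. The footnote to Table A has the success rules tested before the failure rules.

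SAP 12 summarises concomitant antifungals as a yes/no item, as days of use, by drug class and in a duration plot. SAP 7.4 lists seven efficacy subgroups, and concomitant antifungal use is not one of them. SAP 16.1.4 has two sensitivity analyses. In the first, "The primary efficacy analysis will be repeated for the PPAS". The second keeps the mITT and relaxes only the radiological threshold. SAP 2.5 gives no estimand.

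**The concern.** In a single-arm trial every success in the numerator is read as a result on the study drug. The protocol recognises that a second active agent blurs that reading, yet the analysis plan does nothing with the information it collects on such agents. A reader of the report would see how many patients took a concomitant antifungal and, separately, how many responded, but not how the two overlap.

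This matters because the response rate is to be set beside historical rates (SAP 16.1.3), and Protocol 8.1 foresees that data from the first 100 patients might support initial approval. If combination treatment proves common among responders, the rate describes F901318 with or without other active drugs, and nothing in the planned output would show it.

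**Working it through.** The documents state no figure that depends on this rule. Protocol 8.1 gives no formal sample size, and no response rate is assumed in the readable text. The check is therefore mainly one of reading the rules together, followed by an illustration.

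**Step 1: follow one patient through the rules.** Take an mITT patient on F901318 plus a second agent active against the qualifying pathogen, agreed with the medical monitor, who meets the success criteria at Day 42.

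- *Endpoint (SAP 16.1.1).* The success rules are tested first, are met, and do not ask about co-therapy. The patient is a success.
- *Failure rule.* It names alternative treatment that is needed. An add-on in a patient who is doing well is not named.
- *Primary set (SAP 5.4, 16.1.3).* The mITT has no exclusion for co-therapy.
- *PPAS (SAP 5.5).* It excludes patients with major or critical deviations affecting efficacy, and those who do not complete the main phase. Use that is permitted and agreed is not in itself a deviation.
- *Modified response (SAP 16.1.4) and stable-as-success analysis (SAP 16.1.1).* Each widens the success definition, so each can only raise the rate or leave it unchanged.
- *Subgroups (SAP 7.4).* Disease category, prior antifungal response, immunosuppression, duration of prior antifungal therapy, malignancy, neutropenia and reason for limited options. None is concomitant use.

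The patient is counted as a success, and no planned table shows it. By contrast, SAP 17.1.1 does summarise pharmacokinetics by concomitant-medication group.

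**Step 2: illustrate the possible size.** Inputs:

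- n = 200, the planned enrolment (Protocol 8.1), and n = 100, the initial analysis. Both are used as if all were mITT.
- Observed success rate r: an assumption, 30% to 50%, with 40% shown in the table.
- Share q of successes who had an active add-on: an assumption, 5% to 30%.
- Interval: exact Clopper-Pearson, as in SAP 16.1.3. The lower limit is the 0.025 quantile of Beta(x, n−x+1); the upper is the 0.975 quantile of Beta(x+1, n−x).

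With x = n × r successes, counting the affected ones as failures leaves x × (1 − q), so the rate falls by r × q.

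| Observed | q (number moved) | Result | 95% CI |
|---|---|---|---|
| 80/200 = 40.0% (33.2–47.1) | 5% (4) | 76/200 = 38.0% | 31.2–45.1 |
| | 10% (8) | 72/200 = 36.0% | 29.4–43.1 |
| | 20% (16) | 64/200 = 32.0% | 25.6–38.9 |
| | 30% (24) | 56/200 = 28.0% | 21.9–34.8 |
| 40/100 = 40.0% (30.3–50.3) | 10% (4) | 36/100 = 36.0% | 26.6–46.2 |
| | 30% (12) | 28/100 = 28.0% | 19.5–37.9 |

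Over the whole assumed range the fall runs from 0.30 × 0.05 = 1.5 points to 0.50 × 0.30 = 15 points.

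**The case against.** The plan has real controls.

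- Protocol 5.9.2.1 requires agreement with the medical monitor, asks that combinations be minimised, and has patients on isavuconazole or posaconazole switched to fluconazole, which it describes as inactive against moulds.
- Protocol 5.1 and 6.3 keep patients on study drug through Day 42 if antifungal prophylaxis is anticipated after success.
- Most routes in inclusion criterion 7 require that alternatives be ineffective or contraindicated, which limits how often a fully active partner drug exists. Criteria 7f and 7g are looser.
- Need for alternative treatment is a failure, and so is recurrent or emergent infection that needs additional treatment.
- PPAS exclusions are reviewed case by case, and SAP 5.1 allows factors other than deviations to be considered.
- Protocol 8.8 leaves room for further subgroup summaries.
- The primary objective is descriptive, the historical comparison is reported outside the CSR, and the DRC Charter and data review plan are not available to the reader.

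These points narrow the gap to add-on use in responders, and they may make it small. They do not close it. A permitted add-on in a responder still counts as a success. A case-by-case review is not a prespecified rule, and because the PPAS also drops non-completers, its contrast with the mITT would not isolate co-therapy. The optional subgroups of Protocol 8.8 became a fixed list in SAP 7.4 without this one. As to the Charter, Protocol 8.2.2 says that the DRC response criteria will be specified in the SAP, and no such rule appears there.

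**Conclusion.** The point holds as an omission in the analysis plan: the protocol names the threat, the data are collected, and no analysis uses them for Day 42 response. It is a cheap improvement, not a flaw that invalidates the primary analysis. The figures above rest wholly on assumed rates. They are also a worst-case bound, since they treat every affected success as owing nothing to F901318.

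A reader might infer more than the documents support:

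- *That the protocol forbids such co-therapy and the analysis ignores a breach.* The text calls avoidance important, then permits use. This is a stated compromise.
- *That the response rate is inflated by a known amount.* No frequency of use is given, nor any response rate among users. Upward bias is plausible but not established, since sicker patients may be the ones given combinations.
- *That add-on drugs explain successes in* L. prolificans. Protocol 5.9.2.1 does give adding terbinafine as an example. But Protocol 2.1.1 says that no current agent is reliably active against this fungus, and criterion 7a takes it as resistant to all licensed agents.
- *That patients switched for failing therapy are counted as successes.* The order of testing in Table A could be read that way, but SAP 16.1.1 carries patients withdrawn for an unsuccessful outcome forward as failures.

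**What to change.** Add to SAP 16.1.4, for DRC-adjudicated Day 42 response in the mITT with exact 95% intervals:

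1. Response by use (yes/no), between first dose and Day 42, of a systemic antifungal with known or potential activity against the qualifying pathogen, overall and by DRC disease category.
2. A conservative sensitivity analysis that counts successes with such use as failures.

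State and justify in advance any grace period or minimum duration. This is needed because SAP 12 classes a drug as concomitant even if it stopped on the day of first dose, so a brief overlap with prior therapy could otherwise turn a success into a failure. The window should be built from start and stop dates, because the SAP 12 definition follows the dosing period rather than Day 42. Agents given only for *Candida* (such as fluconazole) or for a separate non-susceptible pathogen, and not active against the qualifying pathogen, do not count.

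The cost is one or two tables and an extension of the medical review. SAP 12 plans to confirm which drugs are systemic; activity against each patient's qualifying pathogen would be a new, partly judgemental classification, to be completed before database lock. The resulting figure may be less favourable. If use proves rare, the same tables show that the result is robust. Nothing in patient management changes.

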5.10 Medical Care of Patients after End of Study

The EOS for each patient is defined as the last assessment (scheduled or unscheduled) assigned to the study which that patient completes.

The Sponsor will not provide any additional care to patients after they discontinue F901318 therapy under this protocol because such care should not differ from what is normally expected for patients with IFD.

5.11 Treatment Compliance

Study drug must be administered in accordance with the dose and frequency schedule as described in Section 5.1. Any departures from the intended regimen must be recorded in the eCRF. The Sponsor will inform the Investigator in writing of any changes to the study treatment regimen resulting from ongoing review of study data by the IDSMB. Any Investigator-initiated changes to the study treatment regimen resulting from clinical assessments must be discussed with the MM and approved by the MM.

At each visit, prior to dispensing study drug tablets, previously dispensed study drug tablets will be retrieved by the Investigator or designee and compliance assessed. Patients exhibiting poor compliance should be counselled on the importance of good compliance to the study dosing regimen, and the reason for poor compliance should be investigated. Proper instructions on drug dosing must be provided to the patient by the Investigational staff.

The time of each oral dose will be recorded in a patient dosing diary. Patients who participate as an out-patient at any time on the study will be given the drug dosing diary to take home and complete. Proper instructions on drug dosing and diary completion must be provided to the patient by the Investigational staff. This diary will be reviewed by site staff at each oral drug dispensing visit.

5.12 Study drug Accountability

The Investigator, a member of the investigational staff, or a hospital pharmacist must maintain an adequate and current record of the receipt and distribution of all study drug using the Drug Accountability Form. These forms must be available for inspection at any time.

The Investigator or designee is responsible for recording the date of first and last study treatment administration. The Investigator or designee is also responsible for recording the details required to perform drug accountability and compliance assessments:

- Oral - number of tablets dispensed and the number of tablets returned at each visit, missed doses (including cases of vomiting that may affect dosing) and the reason

Dosing interruptions are to be avoided but may be necessitated by patient care circumstances. The reason for dosing interruption should be recorded wherever possible.

All empty tablet bottles must be kept at the pharmacy or at a place where the study monitor has access to perform drug accountability.

For Out-Patients, oral medication will be supplied in bottles sufficient for 2 weeks of dosing. A maximum of 4 weeks of dosing may be supplied to a patient at any given time without Sponsor approval up to the end of the 84 to 90 day main study phase. Requests for supply to cover more than 4 weeks of dosing will be considered on a case by case basis and must be approved by the Sponsor prior to being supplied to the patient. For those patients receiving ET beyond 84 to 90

days, sufficient medication may be supplied for 8 weeks of dosing. Unused medication may be returned to the patient at the ET visits, to ensure the patient has sufficient study drug to cover possible delays between ET visits. During the informed consent process, the Investigator should discuss with the patient the need to return to the study site between visits for oral drug re-supply. Patients will be given an oral drug dosing diary to take home and complete. This diary will be reviewed by site staff at each oral drug dispensing visit.

All study drug supplies should be accounted for at the termination of the study and a written explanation provided for discrepancies. Patients receiving ET beyond Day 90 should switch to use of drug supplied by that mechanism. All unused study drug supplies and packaging materials are to be inventoried and either returned to [REDACTED] by the Investigator or destroyed locally if suitable facilities are available. The Investigator is not permitted to return or destroy unused clinical drug supplies or packaging materials unless authorized by [REDACTED]

Further details on drug accountability are outlined in the Pharmacy Manual. Study medication must not be used for any purpose other than the study. Study medication must not be used after the retest date unless the study medication is reassessed and its release date extended.

6.0 ASSESSMENTS AND PROCEDURES

The objectives of the study are to describe the efficacy, safety and tolerability of F901318 as treatment for infections due to *Lomentospora prolificans*, *Scedosporium* spp., *Aspergillus* spp., and other resistant fungi in patients lacking suitable alternative treatment options. For the schedule and timing of efficacy and safety assessments, see Table 1.

Assessments of the F901318 PK profile include trough (pre-dose) concentrations to be evaluated throughout treatment, and Intensive PK to be evaluated across a dosing interval [REDACTED] [REDACTED] For the schedule and timing of PK assessments, see Table 2.

6.1 General Considerations

6.1.1 Schedule of Assessments

Day 1 is defined as the first day of administration of study drug. There is no Day 0; Day -1 is the day before administration of first dose of study drug, days preceding this are Day -2, Day -3, etc. Day 2 is the second day of administration of study drug, Day 3 is the third day of administration of study drug, etc.

Study assessments (visits) are scheduled in relation to days of administration of study drug. Screening assessments are to be completed within the 7 days prior to start of treatment unless otherwise specified and agreed with the MM. Assessments scheduled between Day 1 and Day 10 must be completed within the scheduled windows. Subsequent visits are permitted some flexibility to facilitate completion of the assessments; ± 2 days for the visits between study Day 14 and study Day 35 (Visits 8 to 12a) and ± 3 days at study Days 42, 49, 56, 70 and main study phase EOT (Visits 13 to 15, and 17). The Day 84 assessment (Visit 16) is permitted ± 6 days to allow treatment up to Day 90. The post-treatment FU visit (Visit 18) will be performed 4 weeks (± 7 days) after the last dose of study drug (this may not be the last patient visit). For patients planning to receive ET beyond Day 90, the Day 84 visit and the main study phase EOT visit will be combined into a single Day 84/EOS/EOT visit on approximately Day 90. Subsequent visits will be every 4 weeks to assess the safety of continued treatment and to assess the need for further treatment, and there will be a FU visit 4 weeks after ET is completed.

